Participant Symptom Diary

Symptom diary data will be listed and individual symptom scores will be summarized by treatment and visit. The worst severity at each visit from the individual symptoms will also be summarized by treatment group.

The time to improvement (defined as symptoms becoming 0=absent or 1=mild; if baseline is mild, then improvement is defined as symptoms becoming absent) in all items and by individual item will be summarized using the Kaplan-Meier method and compared between randomization arms using a log-rank test. The median time to improvement and the cumulative probability of improvement over time with 95% confidence intervals will be provided by treatment group. Additional statistical models will be explored to assess the between group difference. Details will be provided in the SAP.

WHO 9-Point Ordinal Scale and COVID-19 Related Medical Visits

Ordinal Scale Clinical Improvement data will be listed and summarized by treatment. If data permit, the time to hospitalization/death will also be derived and summarized using the Kaplan-Meyer method.

The proportion of participants who require additional medical visits (including telemedicine visits and hospitalization) related to COVID-19 will be summarized by treatment group and compared between active drug versus placebo using a risk difference and corresponding 95% CI.

Safety

All safety data will be provided descriptively by dose group and scheduled time of assessment where appropriate. Adverse events will be coded using the Medical Dictionary for Regulatory Activities (MedDRA). An AE is considered treatment-emergent if it begins or worsens in severity after the first dose of randomized study drug. The number and percentage of subjects with treatment-emergent AEs will be tabulated by system organ class (SOC) and preferred term. Additional AE summaries will be provided by severity, drug related AEs, AEs leading to study drug discontinuation, and serious AEs.

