This endpoint will be derived similarly to the time to symptom resolution.

• Time to patient reported returned to the (Pre-COVID) health

This endpoint will be derived similarly to the time to symptom resolution.

• Time to resolution of upper respiratory tract symptoms (based on the worst severity of the 5 symptoms measured: Cough, Shortness of breath, Sore throat, Nasal obstruction and Nasal discharge)

This endpoint will be derived similarly to the time to symptom resolution.

• Time to resolution of common COVID symptoms (based on the worst severity of the 13 symptoms measured: Cough, Shortness of breath, Feeling feverish, Muscle aches, Diarrhea, Vomiting, Nausea, Headache, Sore throat, Nasal obstruction, Nasal discharge, Fatigue and Chills)

This endpoint will be derived similarly to the time to symptom resolution.

• Time to resolution of common COVID symptoms (based on the worst severity of the 12 symptoms measured: Cough, Shortness of breath, Feeling feverish, Muscle aches, Diarrhea, Vomiting, Nausea, Headache, Sore throat, Nasal obstruction, Nasal discharge and Chills)

This endpoint will be derived similarly to the time to symptom resolution.

• Time to resolution of Cough

This endpoint will be derived similarly to the time to symptom resolution.

• COVID related medical visit

A subject is considered to have a COVID related medical visit if the subject meets any of the following:

- 1. Hospitalized based on the Hospitalization CRF or any outpatient medical visit (including telemedicine visits)
- 2. Answered "Yes" to the Diary question 'Sought urgent medical care at an emergency room or clinic'
- 3. Answered "Yes" to the Diary question "Been hospitalized for at least 24 consecutive hours"

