9.5. COVID Related Medical Visit

The number and percent of subjects with a COVID medical visit will be presented for each treatment group.

The number and percent of subjects hospitalized during the study will also be summarized by treatment group.

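### SAP 5.5.3 counts care for any cause as COVID-related medical visits, and SAP 9.5 drops the protocol's risk difference; neither change is declared

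*SAP*

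**What the plan says.** Protocol 10.8 (Pooled Analyses, clinical outcomes) says that the proportion of participants needing "additional medical visits (including telemedicine visits and hospitalization) related to COVID-19 will be summarized by treatment group", and that this will be "compared between active drug versus placebo using a risk difference and corresponding 95% CI".

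SAP 5.5.3 derives the outcome as follows: "A subject is considered to have a COVID related medical visit if the subject meets any of the following". The first criterion is "Hospitalized based on the Hospitalization CRF or any outpatient medical visit (including telemedicine visits". The other two are diary answers of yes to "Sought urgent medical care at an emergency room or clinic" and to "Been hospitalized for at least 24 consecutive hours".

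SAP 9.5 gives the analysis: "The number and percent of subjects with a COVID medical visit will be presented for each treatment group". It adds a count of hospitalized subjects but no difference between arms and no interval.

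SAP Section 1 states that the SAP supersedes the protocol's statistical section and that substantial differences will be identified. SAP Section 11 identifies two: the unstratified log-rank test, and the dropping of statistical comparisons of safety endpoints in Part 1. It does not mention medical visits.

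**The concern.** The label and the rule describe different outcomes. A subject who makes one telemedicine call about an unrelated problem meets the first criterion and is tabulated as having had a COVID-related visit. A visit for a suspected side effect meets it too, so a tolerability event could be read as part of an efficacy outcome.

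Because the SAP governs, the wider rule is the one that will be programmed. A reader of the report would take the row to be the protocol's outcome, since Section 11 gives no warning that it has changed. The same reader would look for the protocol's risk difference and interval and find only percentages.

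**Working it through.** **Step 1: is there a filter elsewhere?**
- Protocol 3.2 has staff record hospitalizations and outpatient visits, including telemedicine, since the last visit. It sets no condition on cause.
- Protocol 6.2.10 has participants log urgent visits and hospitalization in the diary, again without a condition on cause. It also foresees referral for worsening illness whatever the cause.
- Protocol 8.1 foresees participants seeking care for concerning adverse events.
- Neither document describes an item recording whether a visit was related to COVID-19.

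So the documents contain no filter, and they do contain routes by which unrelated visits would arise. The eCRF and the full diary questions are not supplied.

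**Step 2: inputs for the size.** The documents give no visit rates, effect size or power for this outcome, so there is no planned figure to reproduce. The following are assumptions:
- true COVID-related visit risks, placebo v active: 10% v 5%, 20% v 10%, 30% v 15%;
- risk u of an unrelated visit, independent of COVID-related visits: 5%, 10%, 20%.

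**Step 3: unrelated visits balanced between arms.** The observed risk in an arm with true risk p is

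p′ = 1 − (1 − p)(1 − u) = p + u(1 − p).

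Subtracting placebo from active gives RD′ = RD × (1 − u).

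| True risks (placebo v active) | True RD | u = 5% | u = 10% | u = 20% |
|---|---|---|---|---|
| 10% v 5% | −5.0 | 14.5% v 9.75%: −4.75 | 19.0% v 14.5%: −4.5 | 28.0% v 24.0%: −4.0 |
| 20% v 10% | −10.0 | 24.0% v 14.5%: −9.5 | 28.0% v 19.0%: −9.0 | 36.0% v 28.0%: −8.0 |
| 30% v 15% | −15.0 | 33.5% v 19.25%: −14.25 | 37.0% v 23.5%: −13.5 | 44.0% v 32.0%: −12.0 |

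Risk differences are in percentage points. In the first row the loss is 0.25, 0.5 and 1.0 point.

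**Step 4: unrelated visits not balanced** (true risks 20% v 10%, RD −10.0).
- Unrelated visits 10% on placebo and 20% on active, for example from side-effect visits: 0.20 + 0.10 × 0.80 = 0.28, and 0.10 + 0.20 × 0.90 = 0.28. RD = 0.
- Unrelated visits 10% on placebo and 5% on active: 0.28, and 0.10 + 0.05 × 0.90 = 0.145. RD = −13.5 points, larger than the truth.

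**Step 5: precision of the protocol's interval.** Take 118 active and 54 placebo from the sample assignment table in protocol Section 3. The half-width is 1.96 × √[p′(1 − p′)/54 + q′(1 − q′)/118], with p′ the observed risk on placebo and q′ on active. For true risks of 10% v 5% it is 8.9 points with no unrelated visits, and 10.8, 12.2 and 14.2 points at u = 5%, 10% and 20%. The added events widen the interval as well as shrinking the difference. The outcome is imprecise even when correctly defined (5.0 ± 8.9 points).

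**The case against.** **The stakes are low.** Medical visits are not among the objectives or endpoints in protocol 10.3 or SAP Section 2. SAP 9.5 plans a descriptive row with no test, and protocol 10.8 itself rules out formal hypothesis tests for the pooled analyses. This stands and limits the severity. It does not make the row's label correct.

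**The forms are unseen.** SAP Section 1 says to read the plan with the eCRF. The two diary items are fragments that may follow a question limiting them to COVID-19, and the outpatient page may be limited in the same way. This is a fair reason for moderate rather than high confidence about what will actually be counted. If such a limit exists, the SAP should say so.

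**An all-cause count is a reasonable measure.** It is objective and avoids judging cause, which brings its own misclassification. This also stands, and it is why relabelling is an acceptable remedy. It does not support keeping the COVID-related label.

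**A stronger reading is tempting:** that the rule biases the treatment comparison toward no effect, and by a lot. With assumed risks of 10% v 5%, a risk ratio of 0.50 would become 0.67, 0.76 and 0.86 at u = 5%, 10% and 20%. The documents do not support that reading. The SAP plans no comparison on this outcome, and the protocol's scale is the risk difference, on which the same assumptions cost 0.25 to 1.0 point. Dilution also requires unrelated visits to be balanced. Blinded randomization makes that plausible for background care, but visits for side effects need not be balanced.

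**Conclusion.** The point holds as a mismatch between label and rule, together with two undeclared departures from protocol 10.8: the wider definition and the missing risk difference with 95% CI. Followed as written, SAP 5.5.3 produces a row that does not measure what its label says.

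The numerical effect cannot be fixed from the documents, because every visit rate above is assumed. Under balanced, independent unrelated visits at 5% to 20%, the risk difference keeps 95% to 80% of its size. Under imbalance it can vanish or grow. A general bias toward no effect is therefore not established.

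This is a supporting clinical outcome, and the primary virology analysis is unaffected. The change is worth making because it is specific and cheap. Confidence is moderate, since the eCRF and diary questions were not available.

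**What to change.** 1. Check whether the eCRF and diary record the reason for each visit or hospitalization.
2. Where they do, set the flag in SAP 5.5.3 only for visits related to COVID-19, under all three criteria. Assign relatedness blind to treatment and before database lock. For Parts 1–6 that means before the lock for the unblinded analysis planned in SAP 4.1. Show all-cause visits as a separate, plainly labelled row.
3. Where they do not, keep the rule and relabel the row *any medical visit*.
4. In either case, add to SAP 9.5 the risk difference, active versus placebo, with its 95% CI as in protocol 10.8.
5. List in SAP Section 11 any departure that remains, including a relabelled outcome.

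The cost is SAP wording, one derived flag and one extra line of output. Step 2 also needs some blinded review of visit reasons, in a trial capped at 204 participants. Its downside is that attribution is a judgement and can itself misclassify; the all-cause row beside it lets a reader see how much depends on that judgement.

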5.6. Missing Data and Outliers

For subjects who prematurely discontinue the study, all available data will be included in the analyses. The planned safety and efficacy analyses will be based on the reported data. An investigation will be made concerning the sensitivity of the results if extreme outliers are detected within the data.

Missing data will not be imputed. However, for adverse events with missing onset dates, treatment emergent flags will be assigned based on the imputation below:

Missing Adverse Event (AE) Onset Date

When a missing or partial onset date has been recorded, the following algorithm will be performed, designed to conservatively assign AEs as treatment emergent when the AE end date is not before the date of first dose.

- If the onset date is entirely missing, then the AE will be assigned as treatment emergent.
- If the year of onset only is provided and the year is the same as the year of first dose of any study drug, then this event would be treatment-emergent. If the year of onset only is

provided and the year is not the same as the year of first dose, then the onset date will be imputed as the 1st of January of that year to determine if the event is treatment emergent.

• If the month and year of onset are provided, and the month and year are equal to the month/year of first dose of any study drug, then this event would be treatment-emergent. In all other cases, the 1st day of the provided month/year of onset will imputed for the onset date to determine treatment emergent. Only if the provided month/year of onset is prior to the month/year of first dose would an event **not** be considered treatment-emergent.

AEs with end date prior to the date of first dose will not be considered treatment-emergent.

AEs with missing severity will be excluded from the by severity summaries. TEAEs with missing relationship to study drug will be considered to be probably related to study drug in the summaries.

Missing Data for SARS-COV-2 RNA Undetectable (Negative) Endpoint

Subjects with missing SARS-COV-2 RNA at a visit(s) will be imputed based on the available non missing SAS-COV-2 RNA data described in the table below:

Visit Before	Visit After	Imputation of Undetectable SAS-COV-2 RNA
BLQ/BLD	BLQ or BLD	Negative
>BLQ	BLQ or BLD	Positive
BLQ/BLD or missing	>BLQ	Positive[1]
Missing	BLQ or BLD	Missing
any value	Missing	Missing

BLD=below the limit of detection. BLQ=below the limit of quantification. [1] Subjects with missing baseline and reported the first post baseline value as >BLQ, the baseline will be imputed as >BLQ (Positive).

Missing Data for SARS-COV-2 Infectious Virus

Subjects with missing infectivity data will be imputed based rules in the table below:

Visit Before	Visit After	Imputed Infectivity Result
Negative	Negative	Negative
Positive	Positive	Positive
Negative or missing	Positive	Positive[1]
Missing	Negative	Missing
any value	Missing	Missing

[1] Subjects with missing baseline and reported the first post baseline value of Positive, the baseline will be imputed as Positive.

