2.2. Study Endpoints

2.2.1. Primary Endpoint

- The viral RNA negativity determined by reverse-transcriptase polymerase chain reaction (RT-PCR) of NP swabs
- Any adverse events (AEs) leading to early discontinuation of treatment; study drugrelated discontinuation of treatment; new Grade 3 or higher AEs (not already present at baseline); study drug-related new Grade 3 or higher AEs and serious AEs

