2.2.2. Secondary Endpoint

- Incidence of Grade 2 or higher AEs and drug-related AEs
- Infectious virus detection in NP swab samples cultured on Vero-cell cultures
- Comparison of spike and RNA dependent RNA polymerase gene sequences using Next Generation sequencing
- Patient reported symptoms of COVID-19
- WHO 9-point ordinal scale
- Concentrations of EIDD-2801 and EIDD-1931

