5.3.3. Safety Population

All subjects who are randomized and take at least 1 dose of study drug. Subjects will be analyzed according to the treatment they actually received. All the safety analyses will be performed using the safety population. The patient diary and clinical outcome (Ordinal Scale Clinical Improvement, medial visit) data will also be analyzed using the safety population.

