8.2. Adverse Events

Adverse events will be coded using MedDRA[®] (Medical Dictionary for Regulatory Activities) Version 23. Any events reported after the initiation of study treatment and up to 14 days after the last dose of study treatment are defined as treatment-emergent AEs (TEAEs). AEs started more than 14 days after the last dose of study treatment will be considered post treatment and will be summarized separately

Adverse event summarizes will summarize only TEAEs. Adverse events will be categorized by TEAE, serious TEAE (SAE), death, and discontinuation. These categories will be further summarized by the causal relationship to study drug (Related and Possible related will be grouped together as Related; AEs Reported as Unlikely and Not Related will be grouped together as Not Related).

The Investigator will provide an assessment of the intensity of each AE. Intensity will be assessed in terms of severity (mild, moderate, severe, potentially life-threatening or death). Subjects will be counted once and summarized under their highest severity within a SOC and PT.

The following TEAE summary tables will be prepared:

• Overall Summary of TEAEs (Any TEAE, TEAE Related to study drug, Grade 2 or higher TEAE, Grade 3 or higher TEAE, Drug related TEAEs, Drug related Grade 3 or higher

TEAE, TEAEs leading to study drug discontinuation, Drug related TEAEs leading to study drug discontinuation, Serious TEAE, TEAE leading to death)

- Summary of TEAEs by SOC and PT
- Summary of TEAEs by maximum severity SOC, and PT
- Summary of Grade 2 or higher TEAEs by SOC and PT
- Summary of Grade 3 or higher TEAEs by SOC and PT
- Summary of Drug Related Grade 3 or higher TEAEs by SOC and PT
- Summary of Drug Related TEAEs by SOC, and PT
- Summary of TEAEs resulting in discontinuation from study drug by SOC and PT
- Summary of Drug Related TEAEs resulting in discontinuation from study drug by SOC and PT
- Summary of Serious TEAEs by SOC and PT
- Summary of Drug Related Serious TEAEs by SOC and PT
- Summary of Post Treatment AEs by SOC and PT

8.3. **Pregnancies (as applicable)**

If any female subjects become pregnant during the study, a listing will be provided.

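### An adverse event left without a grade can lower, but never raise, the Grade 2+, Grade 3+ and drug-related Grade 3+ counts, and the SAP text plans no worst-case count

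*SAP*

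**What the plan says.** SAP 5.6 sets a general rule, "Missing data will not be imputed", followed by exceptions for AE onset date, AE relationship and the virology results. Severity gets no exception. Its own sentence reads "AEs with missing severity will be excluded from the by severity summaries".

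The two neighbouring AE rules point the other way. The onset-date algorithm is "designed to conservatively assign AEs as treatment emergent when the AE end date is not before the date of first dose". For causality, "TEAEs with missing relationship to study drug will be considered to be probably related to study drug in the summaries".

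Grade enters the safety endpoints directly. SAP 2.2.1 lists "new Grade 3 or higher AEs (not already present at baseline); study drug-related new Grade 3 or higher AEs and serious AEs" among the primary endpoints, and SAP 2.2.2 lists "Incidence of Grade 2 or higher AEs and drug-related AEs" as secondary. SAP 8.2 plans the matching tables, for example "Summary of Grade 3 or higher TEAEs by SOC and PT", together with Grade 2+ and drug-related Grade 3+ versions and a table by maximum severity. On the denominator, SAP 5.3.3 says "All the safety analyses will be performed using the safety population".

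**The concern.** Of the three AE attributes for which SAP 5.6 gives a missing-data rule, severity is the only one whose rule tends toward fewer reported events. An event with neither grade nor relationship would be counted as drug-related, yet could not enter the drug-related Grade 3+ table.

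What is at stake is the reading of small counts. SAP 2.3 and SAP 11 make safety reporting descriptive, so the counts are themselves the result. Protocol 10.9 allows safety data to inform dose choice after each part, when groups are small.

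An ungraded event is not obviously a trivial one. Protocol 7.2 requires an AE to be recorded if it is Grade 2 or higher or if it changed treatment. A recorded event that did not change treatment was therefore probably judged at least Grade 2. Sites may also record milder events, so this is a likelihood and not a certainty.

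**Working it through.** The plan states no figure for this rule, so there is none to reproduce. The check has three steps: direction, scale, and which events remain exposed.

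**1. Direction.** Take one participant with two AE slots. Each has a true grade from 0 (no event) to 4, and each grade is either recorded or missing. At threshold k (2 or 3):

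- True status: event if any true grade is at least k.
- Status under SAP 5.6: event if any *recorded* grade is at least k.

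There are 25 grade pairs × 4 missingness patterns × 2 thresholds = 200 combinations. Let p be the number of grade values at or above k, so p = 3 for k = 2 and p = 2 for k = 3.

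| Pattern | Combinations undercounted | k = 2 | k = 3 |
|---|---|---|---|
| Neither missing | 0 | 0 | 0 |
| Exactly one missing (2 patterns) | 2 × p(5 − p) | 12 | 12 |
| Both missing | 25 − (5 − p)² | 21 | 16 |
| Total | | 33 | 28 |

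The SAP count is below the truth in 33 + 28 = 61 combinations, equal in the other 139, and above it in none. It is equal when, for example, the ungraded event was truly below the threshold or another graded event already qualifies. These are logical cases and not probabilities. Counting every ungraded event as qualifying never fell below the truth, so the SAP count and a worst-case count bracket it.

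**2. Scale.** One missed participant lowers a rate by 1/n. Sizes come from the Protocol synopsis and its projected dose table.

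| Analysis set (SAP 5) | Group | n | 1/n |
|---|---|---|---|
| Part 1 | Full arm | 22 | 4.5% |
| Part 1 | Arm if closed at the minimum of 24 (24/2) | 12 | 8.3% |
| Parts 1–9 | 200 mg (22 + 12) | 34 | 2.9% |
| Parts 1–9 | 400 mg (4 × 12) | 48 | 2.1% |
| Parts 1–9 | 800 mg (3 × 12) | 36 | 2.8% |
| Parts 1–9 | Placebo (22 + 8 × 4) | 54 | 1.9% |
| Parts 1–9 | All active | 118 | 0.8% |
| Parts 2–9 | 200 mg (Part 8 only) | 12 | 8.3% |
| Parts 2–9 | Placebo (8 × 4) | 32 | 3.1% |
| Parts 2–9 | All active (8 × 12) | 96 | 1.0% |

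Doses for Parts 5–9 are provisional, so the per-dose sizes are assumptions.

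Protocol 10.7.3.1 reads safety through the upper limit of a 90% interval. For illustration, I use exact (Clopper-Pearson) two-sided 90% upper limits: the 0.95 quantile of Beta(x + 1, n − x). Moving from 0 to 1 event shifts the limit from 12.7% to 19.8% at n = 22, from 22.1% to 33.9% at n = 12, and from 2.5% to 4.0% at n = 118.

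**3. Which events remain exposed.**

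- Serious events and events that stop treatment have their own tables (SAP 8.2).
- Grade 3 and 4 laboratory abnormalities are tabulated separately (SAP 8.4).
- Related Grade 3 events, and related symptomatic Grade 4 events, should lead to stopping study drug, with stated exceptions (Protocol 8.4 and 8.5). With onset during dosing, they should mostly appear in the drug-related discontinuation table.

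What is left is mainly a non-serious clinical event that did not stop treatment, including one that began after the last dose.

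**The case against.** The strongest answer is that the case should hardly ever arise. Protocol 7.2 requires every reported AE to be graded. Protocol 7.1 has the investigator and medical monitor review all AEs weekly. Protocol 10.10 requires cleaning for primary and secondary outcomes before lock, and SAP 4.2 has questionable values picked up during programming. If a blank grade survived all of this, it would still sit in the any-TEAE table and in the listings by subject (SAP 8). SAP 1 allows supplementary analyses. A severity-missing row may already be in the table specifications, which SAP 12.1 places in a separate document that was not available. Leaving the main tables unimputed is also defensible, because assigning a grade is a bigger step than assuming an onset date.

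All of this stands and settles how large the point is. It does not change the direction of the rule. Nor are the tables a full safeguard: SAP 8.2 counts a participant once, at highest severity, within each preferred term. A graded mild event and an ungraded severe one under the same term give matching totals in the any-TEAE and maximum-severity tables, and only the listing shows the gap.

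Three stronger readings are tempting, and the documents do not support them:

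- *The quoted sentence by itself removes ungraded events from the Grade 2+ and Grade 3+ tables.* Its wording most directly describes the maximum-severity table. It reaches the threshold tables only together with the no-imputation rule.
- *The undercount cannot be bounded.* The individual listings let a reader count ungraded events and derive a bound. The SAP simply does not plan to report one.
- *The rule materially distorts the primary safety result or favours the drug.* Nothing in the documents suggests that grades will be missing often, or more often on active treatment, and no safety hypothesis is tested.

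**Conclusion.** The point holds as a small, cheap improvement. Where a grade stays missing, SAP 5.6 can lower or leave unchanged, but never raise, the number of participants counted in the Grade 2+, Grade 3+ and drug-related Grade 3+ summaries. This contrasts with the cautious handling of onset date and relationship in the same section.

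The expected number of missing grades is probably near zero, but the documents give no figure. The one-participant shifts of 0.8% to 8.3% are therefore a scale and not an estimate. They assume that the participant has no other qualifying graded event, that the ungraded event truly met the threshold, and that the planned and projected group sizes are reached.

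**What to change.** Replace the sentence on missing severity in SAP 5.6 with:

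> AEs whose severity remains missing after query will be shown in a separate severity-missing row in the severity summaries, and, if any occur, a worst-case sensitivity summary will count them as events in the Grade 2+, Grade 3+ and (if related or relationship missing) drug-related Grade 3+ summaries.

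No grade is imputed in the main tables. The cost is one SAP sentence, one extra table row and, only if needed, one sensitivity table. That table may overstate the rate if the ungraded event was in fact mild, and should be labelled as an upper bound. If no grade is missing at lock, no reported count changes.
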